3.1 Primary Variables

The primary efficacy variable is the following:

- Ocular itching evaluated by the subject at 10(± 1), 15(± 1), and 20(± 1) minutes post-conjunctival allergen challenge (CAC) at Visits 3 and 4 (0-4 scale, allowing half unit increments).

3.3 Exploratory Variables

There are no exploratory efficacy variables in this study.

3.4 Safety Variables

The safety variables include the following:

- Adverse Events (AE) (reported, elicited and observed);
- Visual Acuity (VA) at Distance Utilizing an Early Treatment Diabetic Retinopathy Study (ETDRS) chart;
- Slit-lamp Biomicroscopy;
- Intraocular Pressure (IOP);
- Dilated Fundoscopy.

3.5 Statistical Hypotheses

4. Study Design and Procedures

4.1 General Study Design

This is a multi-center, double-masked, randomized, vehicle-controlled, phase 2b study evaluating the efficacy of ADX-102 ophthalmic drops (0.1% and 0.5%) compared to vehicle of ADX-102 ophthalmic drops for the treatment of the signs and symptoms of acute allergic conjunctivitis.

The trial will comprise 4 office visits over a period of approximately 5 weeks. Visits 1 and 2 will be used to select a subject population that responds reproducibly to two CACs administered approximately 7 days apart. Subjects who meet the entry criteria for itching and redness response to CAC at Visits 1 and 2 will be randomized (1:1:1) at Visit 3 (Day 1, Enrollment/Randomization) to receive either ADX-102

ophthalmic drops (0.1%), ADX-102 ophthalmic drops (0.5%), or vehicle of ADX-102 ophthalmic drops bilaterally. Subjects will undergo the 1-hour (+5 minutes) duration of action CAC approximately 1 hour from the time of their study drug instillation. Subjects will return approximately 14 days later for Visit 4 (Day 15± 3, 10-Minutes Onset of Action CAC), at which time they will be treated with the same treatment they received at Visit 3 and challenged approximately 10 minutes after dosing. At Visit 4, final exit procedures will also be conducted and subjects will exit the study.

Study visits will be referred to in all tables and listings as the expected study day corresponding to the visit to enable reviewers to understand the assessment timing without referring to the protocol visit schedule. The following table shows the scheduled study visits, their planned study day (note that there is no Day 0 and that Day 1 corresponds to the day of randomization), and the acceptable visit window for each study visit:

Scheduled Visit	Planned Study Day	Visit Window
Visit 1 (Screening/Titration CAC)	Day -21	+/- 3 Days
Visit 2 (Confirmation CAC)	Day -14	+/- 3 Days
Visit 3 (Enrollment/ Duration of Action CAC)	Day 1	NA
Visit 4 (Onset of Action CAC)	Day 15	+/- 3 Days

4.2 Schedule of Visits and Assessments

The schedule of visits and assessments is provided below.

Visit	Visit 1	Visit 2	Visit 3	Visit 4
Day	-21±3	-14±3	1	15±3
PROCEDURE				
General Assessments				
Informed Consent & HIPAA ¹	X			
Demographic Data ¹	X			
Medical & Medication History ¹	X			
Update Medical & Medication History		X	X	X
Allergic Skin Test	X			
Urine Pregnancy Test	X			X
Randomization			X	
AE Assessment			X	X
Allergen Challenge				
CAC	X	X	X	X
Relief Drop Instillation ²	X	X	X	X
Visual/Systems Exams				
Visual Acuity Utilizing an ETDRS chart	X	X	X	X ³
Slit Lamp Biomicroscopy	X	X	X	X ³

Visit	Visit 1	Visit 2	Visit 3	Visit 4
Day	-21±3	-14±3	1	15±3
Intraocular Pressure	X			X
Dilated Fundoscopy	X			X
Investigational Product (IP)				
IP Instillation			X ⁴	X ⁵
Exit from Study				X

5. Study Treatments

This study consists of three treatments arms:

- ADX-102 Ophthalmic Drops (0.1%);
- ADX-102 Ophthalmic Drops (0.5%);
- Vehicle of ADX-102 Ophthalmic Drops.

5.1 Method of Assigning Subjects to Treatment Groups

All subjects screened for the study who sign an ICF will be assigned a 3-digit screening number that will be entered in the Screening and Enrollment Log. Screening numbers will be assigned in a sequential order beginning with 001. Randomization will be used to avoid bias in the assignment of subjects to treatment and time point, to increase the likelihood that known and unknown subject attributes (e.g., demographics and baseline characteristics) are evenly balanced across treatment groups and across time points, and to enhance the validity of statistical comparisons.

Once a subject meets all qualification criteria at Visit 3 (Day 1), they will be enrolled and randomly assigned to masked treatment using a 1:1:1 (ADX-102 ophthalmic drops [0.1%]: ADX-102 ophthalmic drops [0.5%]: vehicle of ADX-102 ophthalmic drops) assignment ratio. Subjects will be assigned the lowest 4-digit randomization number available at the Investigative site within the appropriate stratum. The randomization number will be stratified by the average post-CAC itching scores [REDACTED] at baseline (Visit 2) to ensure balance for the primary endpoint of ocular itching. No randomization numbers will be skipped or omitted.

5.2 Masking and Unmasking

When medically necessary, the investigator may need to determine what treatment has been assigned to a subject. The investigator should make every effort to contact Ora to discuss the subject's emergency situation and the need to unmask a study subject prior to unmasking the IP.

If the investigator determines that emergency unmasking is necessary, the investigator should identify the given subject's study drug kit which contains a scratch off laminate under which the treatment is identified along with the associated lot number. In order to unmask, the investigator should scratch off the laminate, using a flat object and applying pressure, to reveal the treatment assigned for that subject. The emergency unmasking should be performed by the designated site personnel. The investigator must also indicate in source documents and in the electronic case report form (eCRF) that the mask was broken and provide the date, time, and reason for breaking the mask. Any AE or serious adverse event (SAE) associated with breaking the mask must be recorded and reported as specified in the study protocol. The investigator has the responsibility to contact Ora within 24 hours of breaking the blind.

Subjects will have the IP treatment discontinued immediately if treatment assignment is unmasked and will be discontinued from the study.

6. Sample Size and Power Considerations

7. Data Preparation

All reported study data will be recorded on the eCRFs supplied by Statistics & Data Corporation (SDC) using iMedNet™. Only the Principal Investigator and authorized study staff according to the Delegation of Responsibilities log are entitled to make entries in the eCRF.

After data are entered into the clinical study database, electronic edit checks and data review will be performed. All data validation specifications and procedures are detailed in the Data Validation Manual as a separate document. When the database has been declared to be complete and accurate, the database will be locked. Any changes to the database after data have been locked can only be made with the approval of the Sponsor and Ora in consultation with SDC.

All analyses outlined in this document will be carried out after the following have occurred:

- All data management requirements are met according to SDC standard operating procedures, including data entry, performance of edit and validation checks, documentation and resolution of data queries, and database lock with written authorization provided by appropriate SDC and Sponsor personnel;
- Protocol deviations have been identified and status defined (major/minor deviations);
- Analysis populations have been determined; and
- Randomized treatment codes have been unmasked.

8. Analysis Populations

8.1 Intent-to-Treat

The Intent-to-Treat (ITT) population consists of all subjects who are randomized. All data will be included and no subjects will be excluded because of protocol violations. The ITT population will be analyzed as randomized and will be used for the efficacy analyses.

8.2 Per-Protocol

The Per-Protocol (PP) population is a subset of the ITT population and includes the subjects who completed the study through Visit 4 (Day 15) with no major protocol violations. This population will be analyzed as treated using observed data only for confirmatory analyses.

8.3 Safety

The safety population includes all randomized subjects who received the test article. The safety population will be analyzed as treated and will be used for the safety analyses. No data will be excluded for any reason.

9. General Statistical Considerations

9.1 Unit of Analysis

The subject will be considered the unit of analysis for all variables with exceptions of slit-lamp biomicroscopy and dilated fundus examination. For the variables using subject as the unit of the analysis, the average of both eyes of each subject will be used for statistical summaries and analyses in cases where data are collected for each eye. For slit-lamp biomicroscopy and dilated fundus examination results, the eye will be the unit of analysis and summaries will be provided for all eyes combined.

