10.3.1.4 VISIT 4 (Day 15 \pm 3): 10-Minutes Onset of Action CAC

- *Update of Medical/Medication History*
- *Adverse Event Query*
- *Urine Pregnancy Test (for females of childbearing potential)*
- *Visual Acuity Utilizing an ETDRS Chart:* A clinically significant visual acuity decrease (defined as an increase of 0.22 or greater in logMAR score) from Visit 1 will be considered an adverse event.
- *Pre-CAC Ocular Allergic Signs and Symptoms Assessment:* [REDACTED]
[REDACTED]

- Slit Lamp Biomicroscopy
- Investigational Product Instillation: [REDACTED]
[REDACTED]
[REDACTED]
- Conjunctival Allergen Challenge: [REDACTED]
[REDACTED]
- Post-CAC Ocular Allergic Signs and Symptoms Assessment: Assessment of itching will be made by the subject at 5(± 1), 10(± 1), 15(± 1), 20(± 1), 30(± 1), and 60(± 5) minutes following allergen challenge. [REDACTED]
[REDACTED] at 10(± 1), 15(± 1), 20(± 1), 30(± 1), and 60(± 5) minutes post-challenge (**Appendix 2**).
- Exit Visual Acuity Utilizing an ETDRS Chart: A clinically significant visual acuity decrease (defined as an increase of 0.22 or greater in logMAR score) from Visit 1 will be considered an adverse event.
- Exit Slit Lamp Biomicroscopy
- IOP Measurement: Intraocular Pressure (IOP) will be measured in each eye by contact tonometry. An IOP of ≥ 30 mmHg or an increase of 10 mmHg over baseline (Visit 1) will be considered an Adverse Event.
- Dilated Fundoscopy
- [REDACTED]
- Adverse Event Query
- Study Exit

If a female has a positive pregnancy test during the study, then the investigator will notify Ora immediately. The investigator will follow-up and document the outcome of the pregnancy and provide a copy of documentation to the Sponsor. The investigator will retain these reports together with the subject's source documents and will provide a copy of all documentation to Ora.

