16.2 Visual Acuity (ETDRS)

VA will be measured at every study visit prior to the CAC. For Visit 4, it will be measured again post-CAC. Visual acuity (logMAR) will be summarized by treatment using the average of both eyes for each subject with quantitative summary statistics. The number of subjects with worsening of acuity of 10 letters or more from baseline will also be summarized with counts and with percentages based on the total number of subjects in each treatment group with responses. Results for VA will be presented in a data listing.

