16.4 Intraocular Pressure (IOP)

[figure not shown]
IOP will be measured at Visits 1 (post-CAC®) and 4 (post-CAC) and will be summarized by treatment using the average of both eyes for each subject with quantitative summary statistics. At Visit 4, an IOP of ≥ 30 mmHg or an increase of 10 mmHg over baseline (Visit 1) will be considered an AE; the number of subjects meeting this criteria will be summarized with counts and with percentages based on the total number of subjects in each treatment group with responses. IOP will be listed for each eye at each visit.

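### The VA and IOP threshold counts state no eye rule; under the SAP 9.1 two-eye average, a one-eye loss of 10 to 19 letters or a one-eye rise of 10 to 19 mmHg goes uncounted

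*SAP*

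**What the plan says.** The general rule is in SAP 9.1: "The subject will be considered the unit of analysis for all variables with exceptions of slit-lamp biomicroscopy and dilated fundus examination". For variables analysed by subject, "the average of both eyes of each subject will be used for statistical summaries and analyses in cases where data are collected for each eye". VA and IOP are not among the exceptions.

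SAP 16.2 summarises logMAR acuity on the two-eye average and then adds a count: "The number of subjects with worsening of acuity of 10 letters or more from baseline will also be summarized with counts". It closes with "Results for VA will be presented in a data listing", without saying whether the listing is by eye.

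SAP 16.4 has the same shape. IOP "will be summarized by treatment using the average of both eyes for each subject with quantitative summary statistics". A Visit 4 value of at least 30 mmHg, or a 10 mmHg rise over Visit 1, "will be considered an AE; the number of subjects meeting this criteria will be summarized with counts". It adds that "IOP will be listed for each eye at each visit".

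The protocol's Visit 4 section (10.3.1.4) states the same IOP criterion directly after "Intraocular Pressure (IOP) will be measured in each eye by contact tonometry". The same section makes an acuity decrease of 0.22 logMAR or more from Visit 1 an adverse event, both before the challenge and at exit, and does not name the eye.

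No readable text says that either eye, or the worse eye, decides the two threshold counts.

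**The concern.** A threshold count is there to pick out individual subjects with a marked change. If the changed eye is averaged with an unaffected one, the change is halved before it meets the threshold, so a 10-letter limit acts as a 20-letter limit for a one-eye event. SAP 9.1 gives a positive instruction to average, and neither 16.2 nor 16.4 exempts its count. A programmer who follows the SAP literally would therefore produce the lower count.

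For IOP the count and the AE definition use the same criterion. If the count is run on the average while the investigator judges each eye, the two tables can disagree about the same subject. For VA the count and the AE rule differ in threshold and in reference visit, so some difference is expected anyway. The missing eye rule adds a further one that a reader could not trace.

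**Working it through.** The documents give no expected value for either count, so there is no plan figure to reproduce. The check applies each reading to the stated thresholds.

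**Inputs from the documents**
- Averaging rule: SAP 9.1.
- VA threshold, 10 letters: SAP 16.2.
- IOP threshold, at least 30 mmHg or a rise of 10 mmHg (taken as 10 or more): SAP 16.4 and protocol 10.3.1.4.
- Highest eligible Visit 1 IOP, 24 mmHg: protocol exclusion criterion 9.

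**Visual acuity.** Let a be letters lost in the worse eye and b letters lost in the fellow eye (negative for a gain).
- Average reading: counted if (a + b)/2 ≥ 10, that is a + b ≥ 20.
- Either-eye reading: counted if max(a, b) ≥ 10.

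With b = 0, a loss of 10 averages 5.0, 15 averages 7.5 and 19 averages 9.5, none of them counted. A loss of 20 averages 10.0 and is counted. The uncounted range is therefore 10 to 19 letters. It moves with the fellow eye: 10 to 14 if that eye also loses 5, and 10 to 24 if it gains 5.

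**IOP.** Let both eyes start at B, one eye rise by d, and the other stay at B.
- Per eye: B + d ≥ 30 or d ≥ 10.
- Average: B + d/2 ≥ 30 or d/2 ≥ 10.

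For B ≤ 20 the first is met at d = 10 and the second only at d = 20, so whole-number rises of 10 to 19 mmHg change status with the reading. Above 20 the absolute limit takes over, at d = 30 − B per eye and d = 2(30 − B) on the average. The uncounted rises are then 9–17 at B = 21, 8–15 at 22, 7–13 at 23 and 6–11 at 24.

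Examples from an illustrative 16/16 mmHg baseline:

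| Visit 4 | Mean | Mean rise | Per eye | Average |
|---|---|---|---|---|
| 26/16 | 21 | 5 | counted | not counted |
| 35/16 | 25.5 | 9.5 | counted | not counted |
| 36/16 | 26 | 10 | counted | counted |
| 26/26 | 26 | 10 | counted | counted |

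In the second row the affected eye meets both limits and the subject is still not counted. The last row shows that equal changes in both eyes are counted under either reading.

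**Overlap with the VA adverse-event rule.** The documents give no letter-to-logMAR conversion. At an assumed 0.02 logMAR per letter, 0.22/0.02 = 11 letters; assumed values of 0.025 and 0.0167 give 8.8 and 13.2. Read per eye, the AE rule would therefore catch most of the 10-to-19 range. The reference point differs: the AE rule uses Visit 1, while SAP 9.3 sets the safety baseline at the last measurement before first dose.

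**The case against.** The strongest objection is that the count sentences need not inherit the average. In both 16.2 and 16.4 the average is attached to the quantitative summary statistics, and the count follows separately. Acuity, like IOP, is taken by eye (protocol inclusion criterion 7 sets a limit for each eye), and both measures have a Visit 4 AE threshold. A per-eye reading is therefore open for both. It is stronger for IOP, because 16.4 counts subjects who meet an AE criterion on a measure taken in each eye. This stands. A reader might infer that the plan definitely drops one-eye acuity losses and that only IOP is ambiguous. The documents do not support that split, since 9.1 is the default for both counts and is not conclusive for either.

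A second objection is that 9.1's list of exceptions is not exhaustive, because SAP 11.1 reports iris colour by eye. This carries little weight: iris colour cannot be averaged, and its rule is stated expressly.

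Third, events are captured elsewhere. This also stands. IOP is listed by eye and its criterion is an AE. Acuity is listed, the 0.22 logMAR rule makes a Visit 4 decrease an AE, and SAP 16.1 treats any clinically relevant deterioration as an AE. A reader might infer that safety events are lost; they are not.

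Finally, dosing is bilateral, SAP 16 plans no inferential tests on safety variables, and the table list cannot be read. All three limit the weight of the point, but none supplies the missing eye rule.

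**Conclusion.** The point holds at minor severity. SAP 9.1 directs averaging, 16.2 and 16.4 state no exception for their threshold counts, and under that default the one-eye changes shown above go uncounted. The ranges of 10 to 19 letters and 10 to 19 mmHg assume an unchanged fellow eye and, for IOP, equal baselines of 20 mmHg or below. The consequence is confined to two descriptive safety tables, which can read low and disagree with the AE tables. The primary itching analysis is not affected.

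How many subjects this would involve cannot be derived from the documents. Illustrative calculations run from about 0.02 to 2.31 per arm of 50, but they rest wholly on assumed inputs: a per-eye change SD of 3 to 5, a between-eye correlation of 0.3 to 0.9, zero mean change and, for IOP, mean baselines of 14 to 18 mmHg. A spread of more than 100-fold shows that the inputs set the answer, so these figures should not be read as a forecast.

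Confidence is medium, because a table title or footnote that cannot be read might state the eye rule.

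**What to change.** Keep the SAP 9.1 average for all other subject-level summaries and analyses, including itching. Add one exception, in 9.1 or in each of 16.2 and 16.4: for the threshold counts, a subject is counted if either eye meets the criterion, with change measured from that eye's own baseline. Settle this before unmasking so that the choice between readings is not made with the data in view.

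The cost is one sentence and minor programming. No new data are needed, since IOP is measured and listed by eye and the acuity average already requires both eyes. The drawback is that the counts may look slightly less favourable. If the table shells already state an eye rule, the text of 16.2 and 16.4 need only be brought into line with it.

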9.2 Missing or Inconclusive Data Handling

■ [REDACTED]
■ [REDACTED]
■ [REDACTED]

11. **What is the primary purpose of the *Journal of Clinical Endocrinology and Metabolism*?**

This figure is a 2D grayscale heatmap representing a probability density or signal distribution. The distribution is highly complex, featuring multiple distinct peaks of varying intensities. The most prominent peak is located in the central-right portion of the image, with a maximum intensity of approximately 255. To its left, there is a large, elongated peak spanning from the top to the bottom of the frame. In the top-left and bottom-left corners, there are smaller, more localized peaks. The background is dark, with the distribution rendered in white and light gray tones. The overall shape is roughly rectangular but with irregular, jagged edges, suggesting a noisy or high-resolution signal.

The image consists of a series of horizontal black bars of varying lengths, some with internal white notches. A central, more complex black shape is positioned between the top and middle groups of bars. The entire image is rendered in a high-contrast, black-and-white style.

9.3 Definition of Baseline

For the primary efficacy variable (ocular itching scores at 10(± 1), 15(± 1), and 20(± 1) minutes post-CAC), baseline will refer to the time-relevant measure at Visit 2 (e.g., ocular itching at 10 minutes post-CAC at Visit 2 will be the baseline for ocular itching at 10 minutes post-CAC at Visits 3 and 4).

For all safety variables, baseline is defined as the last measurement prior to the first dose of study medication. Change from baseline will be calculated as follow-up visit minus baseline visit.

9.4 Data Analysis Conventions

All data analysis will be performed by SDC after the study is completed and the database has been locked and released for unmasking. Statistical programming and analyses will be performed using SAS[®] Version 9.4 or higher. Output will be provided in rich text format (RTF) for tables and portable document format (PDF) for tables, listings, and figures using landscape orientation. All study data will be listed by subject, treatment, visit and time point (as applicable) based on all randomized subjects unless otherwise specified.

Summaries for quantitative variables will include the number of observations (n), arithmetic mean, standard deviation (SD), median, minimum, and maximum. Minima and maxima will be reported with the same precision as the raw values; means and medians will be presented to one additional decimal place than reported in the raw values. Standard deviations will be presented to two additional decimal places than reported in the raw values. Summaries for qualitative variables will include frequency counts and percentages. All percentages will be rounded to one decimal place (i.e., XX.X%). Differences between active treatment groups and placebo will be calculated as active minus vehicle and change from baseline will be calculated as follow-up visit minus baseline visit.

All statistical tests will be two-sided with a significance level of 0.05 ($\alpha = 0.05$) unless otherwise specified. Confidence intervals (CI) for differences between treatment groups will be two-sided at 95% confidence. All p-values will be rounded to four decimal places; p-values less than 0.0001 will be presented as "<0.0001"; p-values greater than 0.9999 will be presented as ">0.9999".

Unless otherwise specified, summaries will be presented by treatment group and, where appropriate, visit and time point.

9.5 Adjustments for Multiplicity

A series of horizontal black bars of varying lengths, likely representing redacted text or a visual effect. The bars are positioned at different heights and widths, creating a layered effect. The top bar is the longest and spans most of the width of the frame. Below it are several shorter bars, with one notable bar in the middle-left area and another at the bottom right corner.

10. Disposition of Subjects

Subject disposition will be presented in terms of the numbers and percentages of subjects who were randomized, completed the study, and discontinued from the study. Subjects who are not discontinued from the study will be considered study completers. Disposition will be summarized by treatment group and for all subjects.

The number and percentage of subjects prematurely discontinued from the study and the reasons for study discontinuation will be summarized by treatment group for all randomized subjects. The reasons for study discontinuation that will be summarized include: AE, protocol violation, lack of efficacy, administrative reasons, manifest clinically active signs or symptoms of allergic conjunctivitis during the pre-CAC ocular allergic signs & symptoms assessment at Visit 4, sponsor termination of study, investigator decision and other. A subject listing will be provided that includes the date of and reason for premature study discontinuation.

Subject listings will be provided that include informed consent date, inclusion and exclusion criteria violations and exclusions from the PP population.

Protocol violations will be summarized by treatment group for all randomized subjects for each violation category (informed consent, inclusion/exclusion, randomization, subject was not treated with assigned treatment, assessment/procedure not conducted per protocol requirements, missed visit, visit conducted out of window, assessment not done, site failure to report, subject use of prohibited concomitant medication, investigational product stored out of correct temperature control, waiver was granted, other) and severity (min, major) using counts and percentages. Percentages will be based on the total number of subjects randomized in each treatment group. A subject listing will be provided that includes the date

of the violation, the violation description and the classification of whether the violation was judged to be major or minor.

11. Demographic and Pretreatment Variables

